**2.4 Under what criteria would THE ENTIRE STUDY need to be stopped.**

Per IRB, PI, DSMB, or sponsor discretion

**2.5 What are the criteria for breaking the blind/mask?**

Other: Confidentially compromised

**2.6 How will subject withdrawals/dropouts be reported to the IRB prior to study completion?**

IRB-HSR continuation status form

**3. Adverse Event / Unanticipated Problem Recording and Reporting**

**3.1 Will all adverse events, as defined in section 1.1, be collected/recorded? no**

► IF NO, what criteria will be used?

Only adverse events deemed related/possibly related to study

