## Brief Summary/Abstract

The primary objective of this study is to investigate the effectiveness of local antibiotic versus placebo in the prevention of infections in open fractures. The study will assess whether local treatment of open fractures with the antibiotic tobramycin (in addition to standard systemic antibiotics) will decrease the risk and rate of infection, time to fracture union, and rate of re-operation. This will be studied using a randomized controlled clinical trial design in adult population of age 18-70 years who present with open fractures. About 133 subjects will be recruited in this study at UVA. There will also be similar studies performed at University of Florida- Jacksonville and Medical University of South Carolina and we will be performing a collaborative site analysis study with those centers and we will be sharing demographic, infection and treatment information (at either 2 or 6 weeks), and any adverse events that occur.

**Note:** Standard protocols at UVA will be followed for systemic antibiotic administration. No specimens will be collected for research purposes. The patient will otherwise receive the standard of care treatment for their fractures.

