## Data and Safety Monitoring Plan.

### 1. Definition:

#### 1.1 How will you define adverse events (AE) for this study?

An adverse event will be considered any undesirable sign, symptom or medical or psychological condition **even if the event is not considered to be related** to the investigational drug/device/intervention. Medical condition/diseases present before starting the investigational drug/intervention will be considered adverse events only if they worsen after starting study treatment/intervention. An adverse event is also any undesirable and unintended effect of research occurring in human subjects as a result of the collection of identifiable private information under the research. Adverse events also include any problems associated with the use of an investigational device that adversely affects the rights, safety or welfare of subject s.

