### 2.2 List by bullet format a summary of safety tests/procedures/observations to be performed that will minimize risks to participants:

- Renal and eighth cranial nerve function will be closely monitored, especially in patients with known or suspected reduced renal function at onset of therapy and also in those whose renal function is initially normal but who develop signs of renal dysfunction during therapy.
- Urine will be examined for decreased specific gravity, increased excretion of protein and the presence of cells or casts.

- Blood urea nitrogen (BUN), serum creatinine or creatinine clearance will be determined per standard of care during hospitalization.
- Evidence of ototoxicity (dizziness, vertigo, tinnitus, roaring in the ears or hearing loss) or cephrotoxicity will prompt closer monitoring and consultation of ENT and/or the nephrology teams.
- Concurrent and/or sequential systemic or topical use of other potentially neurotoxic and nephrotoxic drugs including: cisplatin, cephaloridine, kanamycin, amikacin, neomycin, polymyxin B, colistin, paromomycin, streptomycin, vancomycin, and viomycin will be avoided. Age and dehydration which increase the risk of toxicity will be monitored. Concurrent use of tobramycin with potent diuretics such as ethacrynic acid or furosemide will be avoided. All patients on diuretics will have them held on the day prior to surgery to avoid complications. Diuretics will be withheld after subject signs Informed consent
- Injecting the drug directly into the fracture site will pose no greater than risk than intramuscular injection of tobramycin.

Clinical care team will be notified of the need to avoid other potentially nephrotoxic or neurogenic agents. A note will be put in Epic to this effect.

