**3.4 What scale will the PI use when evaluating the relatedness of adverse events to the study participation?**

The PI will determine the relationship of adverse events to the study using the following scale:

Related:	AE is clearly related to the intervention
Possibly related:	AE may be related to the intervention
Unrelated:	AE is clearly not related to intervention

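### Events the PI grades clearly unrelated are never recorded, so all-cause adverse event rates and absolute kidney and ear toxicity rates cannot be compared between arms

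*Combined protocol and SAP*

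**What the plan says.** DSMP section 1.1 defines an adverse event broadly: an undesirable sign, symptom or condition counts "even if the event is not considered to be related" to the intervention. Section 3.1 then asks "Will all adverse events, as defined in section 1.1, be collected/recorded? no" and gives as the criterion "Only adverse events deemed related/possibly related to study". It makes no exception for serious events.

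Section 3.4 assigns the judgement: "The PI will determine the relationship of adverse events to the study using the following scale". The scale has three levels. Possibly related means "AE may be related to the intervention"; unrelated means "AE is clearly not related to intervention". Only the last category is dropped.

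The Brief Summary/Abstract says that the sites will share "any adverse events that occur".

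On the drug's risks, the DSMP 2.1 table marks nephrotoxicity in general and ototoxicity as rare. A separate row, marked frequent, covers nephrotoxicity with impaired renal function and with prolonged high dosing. Section 2.2 states that "Renal and eighth cranial nerve function will be closely monitored", with renal laboratory tests done as standard of care while the patient is in hospital. The inclusion criteria admit patients with renal insufficiency, and Biomedical Research item 1 allows other aminoglycosides as systemic prophylaxis.

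**The concern.** A placebo arm allows causality to be judged by comparing event counts between arms, without deciding the cause of each case. Section 3.1 puts a case-by-case causal judgement ahead of recording. In these patients a creatinine rise or a hearing complaint often has another ready explanation: a systemic aminoglycoside, or kidney disease present at entry. If the PI settles on that explanation, the event does not enter the adverse event data and cannot be reclassified from those data after unblinding.

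At stake is what the trial can say about safety at the end. A count of related or possibly related events is not an all-cause count. A low count could reflect few events or many exclusions, and the data would not show which. A true excess on tobramycin would also be harder to see.

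**Working it through.** **The plan's own figure.** The documents give no figure for safety. The only design figure is 60 per group for infection (10% vs 1%, one-sided 0.05, 70% power). With pooled variance:

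n = [1.645·√(2·0.055·0.945) + 0.524·√(0.10·0.90 + 0.01·0.99)]² / 0.09² = (0.530 + 0.166)² / 0.0081 ≈ 60.

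It reproduces, and this point does not change it.

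**What the rule discards.** Sections 3.1 and 3.4 together keep grades 1 (related) and 2 (possibly related) and drop grade 3 (unrelated). Let f be the share of events that pass, and take f as equal in both arms, as expected if the grader does not know the arm. True rates p_T and p_C then appear as f·p_T and f·p_C.

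- The ratio is unchanged: f·p_T / f·p_C = p_T / p_C.
- The difference shrinks to f·(p_T − p_C).
- The absolute rates cannot be recovered, because f is unknown.

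**Illustration.** Inputs: 66 per arm (133 enrolled, divided by two and rounded down) and true renal or ear event rates of 12% and 3%. The rates and f are assumptions; neither is in the documents. Expected counts are 66·0.12·f and 66·0.03·f. Power is for a one-sided Fisher exact test at 0.05, by full enumeration.

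| Share passing, f | Expected events, tobramycin vs placebo | Power |
|---|---|---|
| 100% | 7.9 vs 2.0 | 52.5% |
| 90% | 7.1 vs 1.8 | 46% |
| 80% | 6.3 vs 1.6 | 40% |
| 50% | 4.0 vs 1.0 | 18% |
| 25% | 2.0 vs 0.5 | 3% |

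The apparent rate ratio is 4 in every row. The apparent difference falls from 9 points at f = 100% to 4.5 at f = 50%.

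**Sensitivity to the assumed rates.** At 60 per arm, with a two-sided normal approximation, background risk of 2 to 10% and an excess of 5 to 10 points, power is 13 to 58% with all events recorded, 8 to 32% if half pass and 6 to 18% if a quarter pass. At 3% vs 1% and 66 per arm (one-sided Fisher), it is only 2.6% with every event recorded.

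**Zero events.** If all detected events are recorded and none is seen in 66 patients, the one-sided 95% upper bound is 1 − 0.05^(1/66) = 4.4% (4.9% for 0 of 60). This bounds the rate of events detected under the section 2.2 monitoring. Zero recorded events under section 3.1 bounds only the rate of events that also pass the filter.

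**The case against.** A reader might infer that the arms cannot be compared on safety at all. The documents do not support that. Statistical Considerations item 1 blinds the subject and the injecting surgeon, so a filter applied without knowledge of the arm falls on both arms alike and leaves the expected ratio intact. One qualification is that the text does not say outright that the PI grading events is blinded, and the key may be held by the pharmacist or one other named person.

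A reader might also infer that only events judged to be caused by the drug are kept. The rule also keeps possibly related events. A creatinine rise in a patient who also receives systemic gentamicin has two candidate causes and would naturally be graded possibly related. If the scale is applied as written, f may be high and the loss modest. This stands, and it is why the table includes 80 and 90%. But the grade remains a single judgement with no stated thresholds, and the discarded share would not be known.

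Sections 1.1 and 3.1 might be read as contradictory. They are not: a broad definition followed by a declared subset is coherent. Only the Abstract's sharing statement fails to fit section 3.1.

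The frequent row in the risk table should not be read as the expected rate in this trial, because it also covers prolonged high dosing. Rates of 12% vs 3% are hard to square with toxicity marked rare, and at lower rates the trial has little power whatever the recording rule. That also stands; the table is an illustration only.

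Finally, Statistical Considerations item 5 plans only a primary analysis, and medical-record review up to one year may leave discarded events traceable in source records. This reduces the harm, but tabulating events by arm is a minimal expectation, and searching charts afterwards is a poor substitute for recording events at the time.

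**Conclusion.** The concern holds in a limited form. Section 3.1 leaves unrecorded any event, serious or not, that the PI grades clearly unrelated. The trial therefore gives up the all-cause comparison and the absolute rates of its named toxicities, and it loses some power to see an excess. Comparison of recorded events by arm survives.

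The size of the power loss cannot be fixed from the documents. On the assumed 12% vs 3% it runs from about 6 to 13 percentage points if 90 to 80% of events pass, to about 35 points if half pass. These figures assume the same pass share in both arms and that drug-caused and background events pass equally often. If the grader could pick out drug-caused events, the loss would be smaller. The finding itself rests on the recording rule and on its mismatch with the Abstract, not on these rates.

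**What to change.** Amend DSMP section 3.1 so that the following are recorded in both arms regardless of judged relatedness: all serious adverse events, and all detected renal, vestibular/auditory and neurotoxic events of the kinds listed in sections 2.1 and 2.2. Keep the section 3.4 grade as a data column, and tabulate these events by arm, overall and by grade. Reconcile the Abstract's statement on sharing adverse events with the amended rule. Expedited reporting stays as it is.

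The cost is a few lines on the case report form and the data entry. No new tests are needed and the sample size does not change. Two limits remain. Detection still depends on the section 2.2 monitoring, which gives standard-of-care renal tests in hospital and no audiology or follow-up test schedule. The other sites record events under their own protocols, as the Collaborative Site Analysis Studies table notes, so the change at UVA does not by itself make pooled counts comparable.

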**3. How many subjects will be enrolled at all sites? 133**

**4. How many subjects will sign a consent form under this UVa protocol? 133**

**5. Provide an estimated time line for the study. 2 years**

### **Inclusion/Exclusion Criteria**

**1. List the criteria for inclusion**

- Ages 18 – 70 years
- Gustilo Type I,II,IIa open fracture (s)
- Ability to provide informed consent (or proxy consent in cases where subject is temporarily impaired when intubated and sedated)
- Subject should be able to follow up at the scheduled times following surgery
- Subjects who may have compartment syndrome, renal insufficiency, and those who are immunosuppressed regardless of antibiotic administration will also be included in the study
- 

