**2. List the procedures, in bullet form, that will be done for RESEARCH PURPOSES as stipulated in this protocol.**

- Medical record review at baseline and all subsequent study weeks up to 1 year after surgery
- Randomization to Antibiotic ( tobramycin) arm or Placebo before surgery by clinical pharmacy program at UVA.
- Experimental group will have the close wound injected with 80 mg/40mL of tobramycin at the END of surgery
- Control group will have 40 mL 0.9%NS injected into the closed wound at the end of the case
- Follow up at 2 and 6 weeks at the clinic. *These visits to the clinic will coincide with the follow up as in standard of care for open fracture management.*

**3. Will you be using data/specimens in this study that were collected previously, with the use of a research consent form, from another research study? NO**

**4. Will any of the procedures listed in item # 2 have the potential to identify an incidental finding? This includes ALL procedures, assessments and evaluations that are being done for RESEARCH PURPOSES that may or may not be considered investigational. yes**

► IF YES, check one of the following two options:

The examination(s) utilize(s) the same techniques, equipment, etc., that would be used if the subject were to have the examination(s) performed for clinical care. **There exists the potential for the discovery of clinically significant incidental findings.**

- The PI takes full responsibility for the identification of incidental findings:
- The PI will inform the subjects verbally of all incidental findings that are of clinical significance or are of questionable significance.
- A follow-up letter describing the finding should be provided to the subject with instructions to either show the letter to their PC or if the subject has no PCP, the subject should be instructed to make an appointment at UVa or at the Free Clinic.

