## 2. Identified risks and plans to minimize risk

### 2.1 What risks are expected due to the intervention in this protocol?

Expected Risks related to study participation.	Frequency
Nephrotoxicity	 Occurs frequently  Occurs infrequently  Occurs rarely  Frequency unknown
Neurotoxicity manifested by ototoxicity – vestibular and auditory	 Occurs frequently  Occurs infrequently  Occurs rarely  Frequency unknown
Neurotoxicity manifested by numbness, skin tingling, muscle twitching and convulsions (in patients with preexisting renal damage and normal renal function with prolonged exposure to tobramycin)	 Occurs frequently  Occurs infrequently  Occurs rarely  Frequency unknown
Nephrotoxicity in patients with impaired renal function and in those who received high dose of tobramycin for prolonged period	 Occurs frequently  Occurs infrequently  Occurs rarely  Frequency unknown
Violation of subject's privacy and confidentiality	Minimized due to the requirements of the privacy plan in this protocol

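### Adverse events are recorded only if the PI judges them at least possibly related, so counts of local wound events after the 40 mL injection, chiefly leakage or dehiscence managed conservatively, may be incomplete (minor)

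*Combined protocol and SAP*

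**What the plan says.** Section 1.1 of the Data and Safety Monitoring Plan defines an adverse event without regard to relatedness. Section 3.1 then answers no to recording all such events and gives the criterion: "Only adverse events deemed related/possibly related to study". Under section 3.4, "The PI will determine the relationship of adverse events to the study using the following scale". The scale has three grades. The middle grade, possibly related, is met when the "AE may be related to the intervention"; an event is unrelated only when it is clearly so. The Brief Summary/Abstract is wider than 3.1, because it has the collaborating sites share any adverse event that occurs.

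The table in section 2.1, under "Expected Risks related to study participation", lists kidney toxicity, nerve toxicity (including hearing and balance) and loss of privacy. Section 2.2 provides for renal, eighth-nerve, urine and blood chemistry monitoring. On the injection itself it says: "Injecting the drug directly into the fracture site will pose no greater than risk than intramuscular injection of tobramycin". Neither section names a wound or compartment event.

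Both arms receive the same volume after closure. For placebo: "Control group will have 40 mL 0.9%NS injected into the closed wound at the end of the case" (Biomedical Research, item 2). The same item provides for "Medical record review at baseline and all subsequent study weeks up to 1 year after surgery" and for clinic visits at 2 and 6 weeks. Compartment syndrome appears only in the inclusion criteria: "Subjects who may have compartment syndrome, renal insufficiency" and immunosuppression do not bar entry.

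**The concern.** The filter acts when an event is recorded, not when it is analysed. An event judged unrelated leaves no adverse event record that anyone could grade again later. In an open fracture the injury is always a ready rival cause of leakage, dehiscence or compartment syndrome, and nothing in 2.1 or 2.2 prompts the PI to think of the injection.

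Completeness matters because of the design. Since both arms receive 40 mL, an effect of volume alone cannot appear as a difference between arms. That limit follows from the matched placebo, and better recording does not remove it. The pooled count is then the only figure in the trial that can bound how often these events follow the injection, and an upper limit from it is valid only if the count is complete. Complete counts by arm would also allow a descriptive look at local effects of the drug.

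**Working it through.** **Step 1. Where each event would be captured under the current text.**

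| Event after injection | Adverse event record (3.1, 3.4) | Other route |
|---|---|---|
| Return to the operating room for irrigation and debridement | If not judged clearly unrelated | Counted as major infection (Statistical Considerations, item 2) |
| Compartment syndrome with fasciotomy | Same | Surgical procedures sent by other sites (Information from Outside Institution, item 2); record review to 1 year |
| Wound problem treated with oral antibiotics | Same | Counted as minor infection if cellulitis or superficial infection is documented |
| Leakage or dehiscence managed without surgery or antibiotics | Same | No endpoint or procedure list; only whatever the chart happens to note |

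The last row is the main gap.

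**Step 2. What a complete count would show.** The plan states no figure on this point to reproduce. The safety denominator is every injected subject. I take the enrolment target of 133 and assume that all are injected. For 0 events in n subjects, the one-sided 95% exact upper limit is 1 − 0.05^(1/n).

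- n = 133: 1 − 0.05^(1/133) = 0.0223, or 2.2%.
- n = 120 (the planned efficacy analysis set): 0.0247, or 2.5%.
- n = 106 (133 × 0.8, from the 20% loss to follow-up under Subjects): 0.0279, or 2.8%.

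The first is the relevant one, because an event seen before a subject is lost still counts. The other two would apply only if safety were restricted to subjects with complete follow-up.

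**Step 3. What an incomplete count could do (illustration).** Suppose that 3 of 133 had an event. The exact upper limit is the 95th percentile of Beta(4, 130) = 0.057, or 5.7%. If all three were judged clearly unrelated, the adverse event data would show 0 of 133 and 2.2%. This is the extreme case for three events.

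**Step 4. Sensitivity to the share retained.** The documents give neither a rate nor a retained share, so both are assumptions. With true any-cause rate r and share c judged at least possibly related, the expected recorded count is 133rc and the chance of recording none is (1 − rc)^133.

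| r | c | Expected recorded | Chance of none |
|---|---|---|---|
| 1% | 1.0 | 1.3 | 26% |
| 1% | 0.9 | 1.2 | 30% |
| 1% | 0.5 | 0.7 | 51% |
| 5% | 1.0 | 6.7 | 0.1% |
| 5% | 0.9 | 6.0 | 0.2% |
| 5% | 0.5 | 3.3 | 3.4% |

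At 90% retention the change is slight; at 50% it is material when events are rare. At full retention there is none.

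**Step 5. What a comparison by arm could show.** With the planned 60 per group and no events on placebo, two-sided Fisher p is 0.057 for 5 v 0 and 0.027 for 6 v 0. Only a large excess would stand out, so the comparison is descriptive.

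**The case against.** The strongest reply is that the scale is already permissive. Only events that are clearly unrelated drop out, and leakage from a wound just closed and injected with 40 mL is hard to place there, all the more so when the injecting surgeon does not know the arm. Blinding also makes any loss roughly equal between arms. The form expressly allows a no at 3.1 with a stated criterion. The Safety Summary reports use of this route for all open fractures since 2012 with no adverse effects seen. Case report forms are not among the documents and consent pages were removed, so wound fields or local risks may exist there.

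Most of this stands, and it keeps the point small. It does not answer it. A permissive scale still rests on one unprompted judgement, here by an investigator team that already regards the practice as safe, and the experience cited is an impression without a rate. Blinding protects the comparison between arms but not the completeness of the pooled count. Local risks on a consent page would not change the rule in 3.1.

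Three stronger readings are tempting, and the documents support none of them:

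- **That 40 mL is harmful.** No harm is shown anywhere.
- **That limbs with active compartment syndrome are injected.** The inclusion wording might suggest it, but the injection follows wound closure (Biomedical Research, item 1), so admitting such patients does not by itself mean this.
- **That serious local events will go unseen.** Return to the operating room and fasciotomy have other routes, shown in step 1.

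**Conclusion.** The point holds as a minor, cheap improvement. Section 3.1 filters at recording, section 3.4 makes the filter the PI's judgement, and no local wound event is named to prompt it. Counts may therefore be incomplete, chiefly for leakage or dehiscence managed without surgery or antibiotics.

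The size of the loss cannot be estimated from the documents. The figures in steps 3 and 4 rest on assumed rates and retained shares and are illustrative only; if the PI treats every such event as possibly related, nothing is lost. The 2.2% limit assumes 133 injected subjects, complete recording and no events. A reader might infer that the efficacy result or the comparison between arms is biased. The documents do not support that: the filter applies to adverse events and not to the infection endpoint, and it is applied blind.

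**What to change.** - **Recording.** Amend section 3.1 so that wound leakage, wound dehiscence, and compartment syndrome or fasciotomy arising after injection are recorded in both arms through the 6-week visit, whatever their relatedness. Keep the section 3.4 grade on each.
- **Reporting.** Give these events by arm and pooled, in all injected subjects, with an exact upper limit on the pooled rate.
- **Other sites.** Ask them for the same fields, since the Collaborative Site Analysis Studies table leaves serious events to each site's own protocol. Otherwise report the count for UVA only.
- **Expectedness.** Do not add these events to the section 2.1 table unless the plan also says that serious related or possibly related cases stay on the 7-day IRB route in section 3.7. That route covers unexpected events, so listing them as expected could remove them from it.

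The cost is a few case report form fields at visits that already take place. The drawback is that some recorded events will stem from the injury: the pooled any-cause count bounds how often these events occur but cannot separate injection from injury.
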